9.6 Missing Data

With regards to missing data, the built-in loss rate of 17% includes loss of subjects and also loss due to missing data. Thus, with our recruitment of 60 subjects, we should still be able to reach our 50 subject target completing PIPP data at 4 weeks of MBI.

This pilot clinical trial in the R61 phase is sufficiently small in sample size that imputation methods (e.g., missing week 4 PIPP value or sleep duration) are likely to perform poorly, specifically are likely to add substantial noise to the quantification of the Go/NoGo outcomes. The Go/NoGo quantifications will be computed without imputation and compared to the declared thresholds. Detailed infant and maternal characteristics from baseline assessments will be able to well describe the characteristics of those infants with missing data compared to those with complete data.

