4. SELECTION AND ENROLLMENT OF PARTICIPANTS

4.1 Inclusion Criteria

Participants must meet all of the inclusion criteria to participate in this study:

Preterm infant born at 30 weeks (+/- 2 weeks)

Medically stable

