4.3 Study Enrollment Procedures_

Newborns will be recruited from the University of Minnesota Masonic Children's Hospital neonatal intensive care unit (NICU). We will ensure staff in the NICU are aware of the study and post flyers in the NICU to alert neonatology staff to the study's purpose, inclusion criteria, and the pager number needed to contact the study staff regarding potential subjects. The neonatologist will first mention the study to the parents, then ask whether the parents would be willing to further discuss the study with the study investigators. Only parents who express interest in learning about the research study will be approached regarding enrollment of their infant.

The PI and other selected study investigators listed on the IRB will obtain consent. All study investigators who will be obtaining consent will receive training on how to determine eligibility of subjects and how to discuss the study with parents. The study investigator who obtains consent will ensure the parents understand the informed consent process and the requirements of the study. Parents will be informed that they can ask questions about the study at any time and contact information for the study staff will be provided on the consent form.

Once eligibility has been confirmed and consent obtained, subjects will be randomly assigned to the MBI or control treatment cohorts in a 50:50 allocation ratio using randomization tables, stratified by sex and within each stratum use randomly allocated block sizes of 2 and 4, prepared by [name].

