9.2 Sample Size and Randomization

The R61 phase is exploratory. Based on the number of eligible infants and assuming 60% of eligible subjects enrollment, we can feasibly enroll 60 infants in 1.5 years.. This sample size is similar to or larger than other MBI studies in infants.^{21,23,68,107}

The clinical measure Premature Infant Pain Profile (PIPP) at 4 weeks is the primary outcome for the R61-phase pilot clinical trial. With expected recruitment of at least 60 preterms, expected 50 completed PIPPs at 4 weeks represents a loss to follow-up of $(60-50)/60 = \sim 17\%$. Such a loss rate is slightly more conservative than previous studies completed in the University of Minnesota NICU (which has had ~15% loss rates). This sample size is similar to or larger than other previous MBI studies in infants.

With 50 completed PIPPs at 4 weeks, for comparing MBI to control (25 per group), there is 80% power to detect a group difference in PIPP of 2.9 and 85% power to detect a group difference in PIPP of 3.1. These calculations assume a between-infant standard deviation of 3.6, estimated from the placebo group of a recent study of sucrose as an analgesic for pain from a standard-of-care heel lance. These calculations were carried out in SAS with the following code:

proc power;

twosamplemeans test=diff meandiff = . stddev = **3.6** npergroup = **25**

```
power = 0.80 0.85
    alpha = 0.05
run;
```

;

The R61 exploratory phase data from primary outcome clinical measure PIPP at 4 weeks will be utilized to assist in planning of the R33 phase. The associations of baseline characteristics (infant, e.g. birthweight, and maternal pregnancy history, etc) may inform the design of the R33 phase. For example, these secondary analyses might indicate that we should stratify randomization in the R33 phase by a dichotomized infant birthweight. These analyses, using linear models or non-parametric alternatives if needed (e.g., measures are highly skewed), will use both intervention groups and we will examine the magnitudes of associations in each group and, if appropriate, in the pooled groups.

Treatment Assignment Procedures

Once eligibility has been confirmed and consent obtained. Randomization will be accomplished through the use of randomization tables, stratified by sex and within each stratum use randomly allocated block sizes of 2 and 4. These will be prepared by the study statistician ([name]).

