Measure 3: PIPP scores comparing MBI to controls during a painful procedure. The premature infant pain profile (PIPP) is well established and has undergone extensive psychometric testing. Music creates a sense of familiarity and security in preterm infants and redirects their attention away from the painful stimulus; thus, PIPP scores will be used to measure if MBI has an effect on pain response in comparison to controls.

Statistical Analysis: The PIPP will be scored at 3 age timepoints (30 weeks, 32 weeks, 34 weeks). At each timepoint, average PIPP among MBI infants will be compared to average PIPP among control infants. Milestone threshold will be reached if MBI cohort PIPP scores are \geq 1 point lower than controls at any 1 or more of the scoring points.

Measure 4: Central EEG amplitude changes comparing MBI to controls during a painful procedure. The heel lance painful procedure has been shown to evoke central EEG activity with significantly higher amplitudes, $\ge 10 \ \mu\text{V}$ in infants. EEG will be used to measure amplitude changes in central EEG activity to determine if MBI alters responses to a painful procedure.

Statistical Analysis: Three quantifiable changes in central EEG amplitudes will be collected - one for each age timepoint at which a heel lance is done (at 30, 32, and 34 weeks). Within-infant central EEG amplitude differences between heel sticks and resting states will be computed. Average central EEG amplitude change (heel-stick minus resting-state) among MBI infants will be compared to controls. Milestone threshold is reached if $\geq 10 \ \mu V$ attenuation in central EEG amplitudes occurs with a painful procedure in the MBI cohort compared to controls in any of the serial EEGs.

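### The serial milestones (Measures 1, 3 and 4) rest on unadjusted available-case arm means, although a likelihood-based repeated-measures model needs no imputation and would use the earlier scores, sex and gestational age at birth

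*Combined protocol and SAP*

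**What the plan says.** Section 9.5 defines three serial milestones: sleep duration at four EEGs (Measure 1), PIPP at three timepoints (Measure 3) and the change in central EEG amplitude at three heel lances (Measure 4). Each compares arm averages. For PIPP, at each timepoint, "average PIPP among MBI infants will be compared to average PIPP among control infants", and the milestone is met if MBI is at least 1 point lower at any of them. Measure 2 (ERP) is measured once.

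Section 9.6 argues that imputation would add noise in so small a trial and concludes: "The Go/NoGo quantifications will be computed without imputation and compared to the declared thresholds". Infants with missing data are to be described against those with complete data. The section also states that "the built-in loss rate of 17% includes loss of subjects and also loss due to missing data".

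Section 9.2 names PIPP at 4 weeks as the primary outcome. Its linear models are secondary analyses of baseline associations, meant for planning the R33 phase. Section 9.3 (populations) is marked not applicable. No repeated-measures model, covariate adjustment of the milestones or confidence interval is specified. Randomization is stratified by sex (4.3), eligibility spans 28 to 32 weeks at birth (4.1), and gestational age is one of the seven scored PIPP items (6.2.4).

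**The concern.** Section 9.6 treats the choice as one between imputing values and using raw averages. A likelihood-based model for repeated measures is a third option. It fills in no values, and it lets an infant's observed earlier scores inform the contrast at a visit that the infant misses. The reason given in 9.6 therefore does not exclude it.

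Two things are at stake. The first is precision: a Go or NoGo is declared from a point estimate out of about 25 infants per arm, and strong prognostic information is left unused. The second is robustness. Infants at the same visit can differ by four weeks in maturity. If those missing differ systematically in maturity or earlier pain scores, and differ more in one arm than in the other, the raw difference moves towards or away from the threshold. Describing the missing infants afterwards does not correct the figure.

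**Working it through.** **Inputs from the documents.** Section 9.2 gives 25 completed PIPPs per arm at 4 weeks and alpha 0.05, and "These calculations assume a between-infant standard deviation of 3.6". Section 4.3: "subjects will be randomly assigned to the MBI or control treatment cohorts in a 50:50 allocation ratio"; 60 infants make 30 per arm. Loss is 10/60 = 17%, that is 5 per arm. There are three PIPP visits and a 1-point threshold (9.5).

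**Assumed, because the documents are silent.** Within-infant correlation ρ from 0 to 0.7, equal between all visits (compound symmetry) unless stated; the first two PIPPs observed in all infants.

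**1. The plan's own figure.** Section 9.2 claims "80% power to detect a group difference in PIPP of 2.9 and 85% power to detect a group difference in PIPP of 3.1". A two-sided two-sample t-test gives detectable differences of 2.91 and 3.11, so both reproduce. On the normal scale, used below, the 80% figure is 2.85.

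**2. Raw means at week 4.** SE = 3.6 × √(2/25) = 1.018.

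**3. Repeated-measures model, no baseline adjustment.** Let R² be the squared multiple correlation of the week-4 score with the first two: R² = 2ρ²/(1+ρ). Then

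Var = 3.6² × 2 × [(1−R²)/25 + R²/30],

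and the proportional reduction against raw means is R² × (1 − 25/30) = R²/6. At ρ = 0.5, R² = 0.333 and the reduction is 5.6%.

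**4. The same model with a common baseline mean**, valid only if the first score precedes any MBI. With b = ρ/(1+ρ),

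Var = 3.6² × [2(1−R²)/25 + b²(1−ρ²) × 2/30].

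At ρ = 0.5: 12.96 × (0.0533 + 0.0056) = 0.763, SE 0.874.

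| ρ | SE raw | SE model (variance change) | SE with common baseline (variance change) | 80% detectable difference: raw / model / baseline |
|---|---|---|---|---|
| 0 | 1.018 | 1.018 (0%) | 1.018 (0%) | 2.85 / 2.85 / 2.85 |
| 0.3 | 1.018 | 1.006 (−2.3%) | 0.967 (−10%) | 2.85 / 2.82 / 2.71 |
| 0.5 | 1.018 | 0.990 (−5.6%) | 0.874 (−26%) | 2.85 / 2.77 / 2.45 |
| 0.7 | 1.018 | 0.968 (−9.6%) | 0.717 (−50%) | 2.85 / 2.71 / 2.01 |

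If correlation decays with time (AR(1)), the reductions at ρ = 0.5 are 4.2% and 9.4%. With no missing scores, the step 3 model returns exactly the raw differences.

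These SEs treat the covariance as known. In 1,500 simulated trials with an estimated unstructured covariance, the SDs (raw / model / with baseline) were 1.02 / 0.99 / 0.89 at ρ = 0.5 and 1.02 / 1.02 / 1.03 at ρ = 0.

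**5. Gestational age at birth.** Assume it is uniform on 28-32 weeks and that PIPP falls 0.8 point per week. It then carries 0.8² × 4²/12 = 0.85 of the 12.96 variance, about 7%. This overlaps with ρ and is not additive to the table.

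**6. Bias, no true effect.**
- *Loss tied to gestational age.* Under the step 5 assumptions with ρ = 0.5, and missingness differing between arms by 12 or 24 percentage points, the simulated raw difference was 0.13 or 0.23 against a simulation offset of 0.03. That is an error of about 0.1 or 0.2 point. Adjusted for baseline and gestational age, it stayed at the offset.
- *Loss tied to earlier scores.* Suppose the five MBI infants missing at week 4 tend to be the high week-2 scorers, while control losses are unrelated to scores. The raw difference shifts by −0.28, −0.52 and −0.67 at ρ = 0.3, 0.5 and 0.7. The chance of a difference of 1 point or more at week 4 rises from Φ(−1/1.018) = 16% to 25%, 32% and 38%. The likelihood model stays within about 0.05 of zero.
- *The same pattern in both arms.* The shifts cancel and the raw difference is unbiased.

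**The case against.** The strongest reply is that this is an exploratory pilot. Its milestones are deliberately simple point-estimate thresholds, 9.6 gives a reason for not imputing, and a difference in means is transparent. That stands, and it is why this is a point about efficiency and robustness and not an error in a stated figure.

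Three stronger readings are tempting, and the documents do not support them.

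- A reader might infer that the plan is a complete-case analysis that discards infants. It is not. Each timepoint is compared separately, so an infant missing week 4 still counts at the earlier points, each of which can trigger Go. The earlier scores are unused only for the week-4 contrast.
- A reader might infer a large precision gain from using all the scores. Adjusting for baseline and gestational age together, under the assumptions in step 6, cuts the SD from 1.06 to 0.90, or 15%. But baseline adjustment alone, with complete data and ρ = 0.5, gives 1 − √0.75 = 13%. Recovering missing scores gives under 3% of the SE (1.018 to 0.990).
- A reader might infer that the raw means are biased as planned. That requires missingness that differs between arms. Nothing in the documents predicts it: equipment is identical and outcome staff are blinded (6.2.3), and infants who stop the intervention are still followed (section 8). No discharge criterion is given, so earlier departure of the most mature infants is conjecture. With 17% loss overall, a 24-point gap means roughly 5% against 29%.

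The baseline is also uncertain. Randomization comes immediately after screening (6.2.2), the 30-week PIPP is itself a milestone point (9.5), and section 3 describes EEG sessions that combine MBI with the painful procedure. If the first value is taken under MBI, adjusting for it would remove part of the effect.

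**Conclusion.** The point holds for Measures 1, 3 and 4. Their contrasts are unadjusted available-case means, and the reason given in 9.6 does not rule out a model that uses the collected scores and two covariates fixed before randomization. Measure 2, with a single visit, is not affected.

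The certain gain is small. At the planned loss, recovered scores lower the week-4 PIPP variance by 0-10%. Up to 50% is available only if the first PIPP precedes MBI and correlation is high and does not decay over time. The better argument is protection: about 0.1-0.7 point of possible bias against a 1-point threshold, conditional on differential, informative loss. The correlation, its structure, the PIPP slope and the missingness patterns are all assumptions. The 16% and 25-38% chances are for week 4 alone, not for the any-timepoint rule. The change is worth making before unblinding because it is cheap, and because choosing a model after seeing unbalanced loss would be post hoc.

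**What to change.** In 9.5 and 9.6:

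1. Estimate the arm contrast at each visit for Measures 1, 3 and 4 from a likelihood-based repeated-measures model with arm by visit, sex and gestational age at birth. Use an unstructured covariance and include every infant with any observed value. A small-sample degrees-of-freedom correction (for example Kenward-Roger) suits 60 infants.
2. Report each contrast with a 95% CI against the existing thresholds. Measure 1's threshold is a percentage, so state how it is formed from the adjusted means.
3. Keep the raw means as a sensitivity table.
4. State whether the first PIPP and EEG are taken before any MBI. Only if they are, adjust for that value or constrain it to a common mean across arms.
5. Leave the any-timepoint Go rule and Measure 2 as they are. The revision history (version 2.0b) explains that rule as a deliberate search for sensitive periods; moving to the week-4 contrast alone would be a separate design decision.

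Cost: modest extra analysis and no new data. The downside is that the milestone figure becomes model-based and is no longer a simple difference in means.

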10. DATA COLLECTION AND QUALITY ASSURANCE

10.1 Data Collection Forms_

NICU-based study activities. PI, [name], with the assistance of Co-Investigators, [name] and [name], will be responsible for overseeing study implementation and all NICU-based data collection. Specifically, they will oversee the research coordinators who provide day-today supervision of participant informed consent and enrollment, MBI vs control intervention, and outcome assessments including EEGs and PIPPs.

Neurodevelopmental testing. Tracking of study participants after NICU discharge and coordination of follow-up visits will be overseen by PI, [name] with the assistance of study coordinators. ERP testing will be conducted by [name] at the Center for Neurobehavioral Development. Bayley's III Neurodevelopmental testing will be conducted by the psychometrician at the Center for Neurobehavioral Development.

Data coordination and management will involve design of data collection forms in REDCap for NICU and follow-up data. These will be managed by the study coordinators with PI, [name], and Co-Investigator, [name], oversight. REDCap data analysis will be conducted by PI, [name], Co-Investigators, [name], and Biostatistician, [name]. EEG data will be stored in password protected encrypted hard drives by study coordinators. EEG data will be managed by study coordinators and PI, [name]. EEG data analysis will be conducted by PI, [name], and Co-Investigators, [name], [name], and the biomedical engineering graduate student.

Data collected specifically for this study will be for clinical trial research purposes only and will include clinical data regarding the subject's medical history and hospital course including clinical characteristics such as age, daily weight including birthweight, race and any underlying neonatal, perinatal and maternal health conditions. Most clinical data will be obtained from subjects' medical records. In addition, EEG, PIPP, ERP, and neurodevelopmental assessment data will be collected. Study staff will have access to individually identifiable information about the infants enrolled in the study. Data will be collected by the study coordinator and recorded onto case report forms (CRFs). Data from the CRFs will subsequently be entered into the research database located on the encrypted study laptops. The CRFs and the electronic database will only have de- identified information to preserve confidentiality of patients' protected health information. Files that link the study identification number for each subject to the subject's personal information (such as name, medical record number, parents' names) will filed separately and only be accessible to the PI and study coordinators.

10.2 Data Management_

See section 10.1 above.

10.3 Quality Assurance

10.3.1 Training

The PI will ensure all staff are qualified for their study roles and trained on the protocol.

10.3.2 Quality Control Committee

This study will also be monitored semi- annually via independent monitoring services from the Clinical and Translational Science Institute (CTSI) at the University of Minnesota.

CTSI Independent Monitor(s) review study materials (documents, records, Case Report Forms, etc) to assure that the study is conducted, recorded, and reported in compliance with FDA Good Clinical Practice.

10.3.3 Metrics

CTSI Independent Monitor(s) will also ensure that the study is conducted in accordance with the protocol and inclusion/exclusion criteria as approved by the IRB. The goal is to promote and facilitate compliance with Good Clinical Practice through:

- Regular monitoring visits
- Quality assurance
- Data query resolution
- Review of study regulatory files
- Adverse Event/Serious Adverse Event (AE/SAE) reviews
- Compliance consultation services
- Typical review of subject specific documents includes but is not limited to:
 - Signed informed consent/HIPAA documents
 - Case Report Forms (CRFs)
 - Medical records (for AE/SAE)
 - Regulatory binders
 - Communications with FDA/IRB

10.3.4 Protocol Deviations

Protocol deviations will be documented in the study file and those that meet IRB reporting criteria will be reported accordingly.

10.3.5 Monitoring

This research study involves no greater than minimal risk to participants. See above 10.3.2 for above details of monitoring.

11. PARTICIPANT RIGHTS AND CONFIDENTIALITY

11.1 Institutional Review Board (IRB) Review_

The IRB at the University of Minnesota is a fully authorized Institutional Review Board that provides oversight to research conducted at the university. It functions in compliance with the congressional statutes governing Assurance of Compliance with Health and Human Services (HHS) Regulations for Protection of Human Research Subjects. This board will be providing oversight to the current study.

11.2 Informed Consent Forms

The PI and other selected study investigators listed on the IRB will obtain consent. All study investigators who will be obtaining consent will receive training on how to determine eligibility of subjects and how to discuss the study with parents. The study investigator who obtains consent will ensure the parents understand the informed consent process and the requirements of the study. Parents will be informed that they can ask questions about the study at any time and contact information for the study staff will be provided on the consent form.

11.3 Participant Confidentiality

Every effort will be made during this study to ensure confidentiality. Only authorized study personnel and others authorized for regulatory purposes as described in the consent form will have access to this information. Study data will be de-identified and entered by the study coordinators into a password protected, encrypted electronic database for storage, retrieval, and analysis. EEG files will be de-identified and recorded onto a password protected, encrypted computer workstation. Each EEG file will be downloaded onto an encrypted hard drive with one extra backup copy. The EEG files will include video of the child and those who may be caring for the child during the EEG, such as a parent or staff member. There is also sound captured during the EEG but this is not listened to by the investigator. All confidentiality processes, as outlined above, will be followed for all video recordings. In all records, presentations, and manuscripts to be made public, the videos taken during the EEG will be de-identified so not to show the infant's face.

Families will be approached by research staff in private settings e.g. the mother's or infant's private hospital room. All information and data collected for the sole purpose of this study will be kept confidential. Only authorized study personnel and others authorized for regulatory purposes as described in the consent form will have access to this information. Medical information collected during this study will become part of the subject's hospital record, if the information is determined to be pertinent to the subject's medical care or is a usual part of the subject's care (e.g., results of tests ordered by treating clinicians that are also recorded for research purposes). Medical records are available to other health care professionals at the hospital and may be

reviewed by hospital staff in their course of carrying out their responsibilities. However, they are required to maintain confidentiality in accordance with applicable laws and hospital policies. Study information that is not included in the medical record and could be personally identifiable will be under restricted access and viewable only by members of the research team (PI and study coordinators). These research records will not be made available to anyone not on the research team except upon a parent's request or as required by law. Deidentified EEG data will be recorded onto a password protected. encrypted computer workstation. Each EEG file will be downloaded onto an encrypted hard drive with one extra backup copy. Data from various domains will be entered by the study coordinators into an electronic database for storage, retrieval, and analysis. Additional measures needed to ensure restricted access and confidentiality will be considered and implemented as deemed necessary. In all records, presentations, and manuscripts to be made public, information or data will not be personally identifiable. In the case that data or references to specific study patients are used, the patients will only be identified by code in order to maintain confidentiality.

